## 1. Glossary of acronyms

QoL: Quality of Life

App: Mobile application

ADL: Activities of Daily Living

## 2. Introduction:

Stroke continues to be one of the leading causes of death and disability in the Spanish adult population, with the presentation of various sequelae, such as impaired mobility and a consequent reduction in Quality of Life (QoL). These sequelae, which can be chronic, generate significant spending and a saturation of social and health services. With the growth in the number of cases, the development of new rehabilitation approaches and updating to the current social context becomes pertinent, such as the incorporation of telerehabilitation to assist individuals who have suffered a stroke.

## 3. Background and current status of the topic:

Stroke, defined by the World Health Organization as the rapid development of clinical signs of local or global disturbance of brain function, for more than 24 hours or leading to death, without any other apparent cause than vascular origin, it is the most well-known and frequent cerebrovascular disease in the adult population (1). In Spain, according to data from the National Statistics Institute, death in adults from cerebrovascular disease continues to be one of the leading causes of death in our country, with about 30% of cases (2) .

Stroke is also one of the leading causes of disability in the adult population, generating a significant expense and saturation of social and health services, both in the acute and chronic phase, since its symptoms are usually permanent to a greater or lesser extent. degree. Among these symptoms one can find language disorders or cognitive alterations, but the most common is the sensory-motor alteration of the half of the body opposite to the brain injury(3) . These alterations lead to a significant reduction in QoL since they provide the patient with great disabilities in different areas of their life. In 2013,

Schmid et al. Associated the balance deficit and the risk of falls with a low QoL level in patients with stroke in its chronic phase (4) .

Faced with the possible sequelae of stroke, survivors often attend neurorehabilitation programs in which physical therapy, psychology, speech therapy, among others, depending on the needs of the individual, participate. In relation to sensory and motor rehabilitation, which is usually the responsibility of physiotherapy, one of the fundamental therapeutic objectives is to achieve optimal trunk control and sitting balance since it is known that the low performance of the trunk musculature, specifically its delayed and asynchronous activation due to the resulting hemiparesis, is associated with poor postural balance and gait instability (5) . Known studies support the idea that trunk stability plays a critical role in maintaining balance both in sitting and standing, functional mobility, gait, and increased QoL in individuals with stroke (6,7,8).

Being aware of the growth in the number of cases, the impact on the health of individuals and their resulting disability, it would be advisable to study and develop new effective means to respond to the growing demand for individuals with stroke, such as the use of digital technologies for therapeutic exercises to intensify rehabilitation even at home. Its use can facilitate access to information and guidelines for rehabilitative treatment by patients and their families or caregivers, provide greater intensity to therapies and increase the involvement of individuals in the rehabilitation process. On the other hand, it would also allow continuous therapeutic follow-up without the need for displacement and the perpetuation of the rehabilitation of permanent sequelae and their secondary sequelae. With this vision and knowing that the use of electronic and digital devices, such as the smartphone or tablet, is becoming more frequent, it is hoped that these will be considered as a possible therapeutic resource.

From this concept telerehabilitation arises, as a rehabilitation method in which professionals use telecommunications devices to provide intervention, assessment and support strategies for disabled people who are at home. This is a feasible method and has the advantages of providing flexibility of time and space, reducing inequality in medical care, improving the quality of care, and reducing costs in human resources, transportation, and facilities (9) . In the market you can find mobile applications (App) for neurorehabilitation such as language rehabilitation, cognitive disorders and incentives for physical activity. However, these apps are usually incomplete and depersonalized, and

their results compared to conventional therapies in a clinical setting are inconclusive (10) . In a current systematic review, published in 2018, no App has been found that contemplates personalized functional physical rehabilitation for individuals with Stroke (11) . For this reason, it is convenient to find an App that contemplates motor rehabilitation customized to the abilities of users with Stroke.

The idea of introducing telerehabilitation in the physiotherapy services of care for chronic patients, has the intention of improving health care services and optimizing human resources while promoting the rehabilitation process of the sequelae of individuals. Apart from the continuous contact channel between medical personnel and users and means of monitoring clinical evolution, it becomes pertinent to study this type of digital tools as a means of personalized prescription of therapeutic exercise for the home, especially in chronic situations that saturate rehabilitation services. This research study will provide information on the effectiveness of using an App as a means of personalized prescription of therapeutic exercises to be carried out at home, especially lumbopelvic stabilization exercises whose evidence is known. Thus, it is expected to study the level of adherence to telerehabilitation by individuals with stroke in its chronic phase, along with analyzing clinical results related to balance and its influence on participation in Activities of Daily Living (ADL) and QoL.

#### 4. Objectives:

This project has the following proposed objectives:

- To analyze the adherence to the treatment of the App
- To evaluate the effectiveness of an intervention of lumbopelvic stability exercises performed at home, through the use of an App, compared to usual therapy.

#### 5. Hypothesis:

The hypothesis of the present study project is: to. The use of an App, adapted to the abilities and needs of individuals with stroke, improves adherence to its use for carrying out specific therapeutic exercises. b. Muscular stability exercises of the lumbopelvic area performed at home monitored by means of an App improve the

perception of the QoL of individuals who have suffered a stroke in the chronic phase of their evolution compared to the usual follow-up of this type of individuals. c. Muscular stability exercises of the lumbopelvic area performed at home monitored by an App increase the functionality and participation in the ADL of individuals who have suffered a stroke in the chronic phase of their evolution compared to the usual follow-up of this type of individuals. d. Muscular stability exercises of the lumbopelvic area performed at home monitored by an App improve the balance in sitting and standing and reduce the number of falls of individuals who have suffered a stroke in the chronic phase of their evolution compared to the usual monitoring of this type of individuals. and. Muscular stability exercises of the lumbopelvic area performed at home monitored by means of an App improve the gait of individuals who have suffered a stroke in the chronic phase of their evolution compared to the usual follow-up of this type of individuals.

## 6. Material and methods:

For this study, the Farmalarm App of the Inmoven group - Vall d'Hebrón Hospital will be used, adapted and updated by the main researchers of this study. The App will have the "rehabilitation" option where the user can consult the description of the exercise and view a demonstration video so that it can be carried out correctly at home, independently or with the help of a third person. The researchers will be responsible for The researcher of this study will also be registered as administrator of the App with permission to create users, contact them directly through chat or video-call and personalize the exercise program for each user. On the other hand, they will also have permission to consult the use data of the App by users. The App will also contemplate the option of confirming the completion of each proposed exercise and a small survey related to the effort used to complete it. The data obtained from these options will facilitate the customization of the exercise program.

The exercises that will be carried out with the App, in this study phase (Table 1), are described in previous works by the author [name] and colobradores (6). All possible exercises (description and demonstration video) will be included in the administration platform of the App and according to the capabilities of each user, the prescription of some exercises or others will be made, respecting their progression. In this

way, the aim is to personalize the therapeutic exercise program for each user, as well as modify the number of repetitions suggested and add facilitating or hindering suggestions to the same exercise.

Supino	Báscula pélvica antero-posterior Rotación de tronco superior Puente pélvica Puente con movimiento lateral Puente unilateral derecho Puente unilateral izquierdo Rotación del tronco inferior Flexión y extensión de rodillas Puente en pelota unilateral derecha Puente en pelota unilateral izquierda	  
Sedestación	Báscula pélvica antero-posterior Rotación de tronco superior Báscula pélvica medio-lateral Rotación tronco inferior Flexión lateral del tronco Alcance anterior Alcance lateral derecho Alcance diagonal derecho Alcance lateral izquierdo Alcance diagonal izquierdo	  
Sedestación en pelota	Báscula pélvica antero-posterior Rotación de tronco superior Báscula pélvica medio-lateral Rotación tronco inferior Flexión lateral del tronco Alcance anterior Alcance lateral derecho Alcance diagonal derecho Alcance lateral izquierdo Alcance diagonal izquierdo	  

Table 1: Stability exercises of the lumbopelvic region

In this simple blind randomized controlled pilot study, participants will be recruited from users of the rehabilitation center where the study will be carried out (Neurorehabilitation Clinic - Sant Cugat del Vallés). To carry out this study, there is already an agreement signed between the Neurorehabilitation Clinic and the International University of Catalonia.

The following participation criteria have been defined for this pilot study Inclusion criteria:

- Medical diagnosis of stroke with cortical or subcortical, ischemic or hemorrhagic involvement with more than 6 months of evolution
- Clinical symptoms of hemiplegia or hemiparesis
- Over 18 years of age
- Ability to understand and execute simple instructions
- Score equal to or less than 10 in the Spanish version of the Trunk Impairment Scale 2.0
- Be a frequent user of smartphone or tablet. Failing this, the direct family member / caregiver is considered.

Exclusion criteria:

- Appearance of any disease or aggravation of any of the comorbidities that the patient presents that prevents rehabilitation (example: dialysis)
- Suffer a second episode of Stroke.
- Fractures in any of the lower extremities or important structural alterations in the trunk.
- Death

30 participants will be recruited. No sample calculation will be performed as it is a convenience sample for a pilot study and it is a value very close to the total number of users with Strokes of the center where the study will be carried out. Another limiting factor of the sample is that the users will be monitored daily or weekly by an investigator assuming a ratio of 30 users / 1 therapist. In the recruitment process, patients will be informed about the study, they will be asked to sign an informed consent and the randomization between the experimental group and the control group will be done by computerized lottery and with the following interventions:

Experimental Group: Use of App for the daily performance (Monday to Friday) of lumbopelvic stability exercises (Table 1) apart from the usual physiotherapy treatment for 3 months.

Control Group: Regular physical therapy treatment.

The information on the usual physiotherapy treatment will be collected together with the variables to be studied. At the end of the study, the description of the usual treatment, neuromotor development treatment, will be disclosed, which usually includes techniques for modulating the muscle tone of the affected body, postural control exercises, facilitation of functional movement and practice of tasks including walking.

To guarantee the blinding characteristic, the evaluations will be carried out by a third non-investigating person. The following variables will be studied through selected tests and questionnaires:

- Adherence to the use of the App by individuals from the EG: Data extracted by the administration panel of the App and System Usability Scale. Optimal use (100%) is considered 5 days / week, that is, a use from 0 to 20 days in 12 weeks months will be considered low adherence (0-33%), from 21 to 40 days (33-66%) regular adherence and 41 to 60 days (66-100% :) good adherence.
- QoL: EuroQol 5 dimensions 5 levels.
- Participation in AVD: Barthel Index.

- Functionality: Rankin scale.
- Sitting balance: Spanish versions of the Trunk Impairment Scale 2.0 and Function in Sitting Test.
- Standing balance: Spanish version of the Postural Assessment Scale for Stroke Patients, Berg Scale
- Record of the number of falls.
- Gait: stepping section of the Brunel Balance Assessment test and if they reach a score of 6 they will be evaluated with the G-Walk accelerometer (duration of double and individual support, cadence of the step, gait speed, stride length, length of step and elaborate steps).

For statistical analysis, all subjects will be included, regardless of subsequent events such as protocol violations, lost data, or loss to follow-up. Qualitative and quantitative descriptive statistics will be used to characterize the sample depending on categorical (eg.: sex) or numerical (eg.: age) variables. In the analysis of results, the missing data will be imputed applying the imputation criterion of the last observation made. The distribution of the sample will be calculated according to the Shapiro-Wilk test and parametric and / or non-parametric tests will be used to calculate the significance of the results. The significance level (p) will be 0.05, that is, a confidence level of 95% and 5% of acceptable error. For the purpose of this study, it is proposed to analyze the difference between means and standard deviations of the variables both at the initial time and at 6 and 12 weeks. Its statistical significance will be calculated by the Student's t test or the Mann-Whitney U test for paired data. For the analysis of the effectiveness of the interventions, the evolution obtained in the different groups will be compared with the same statistical tests for independent samples. To assess the correlation between variables, the calculation of Pearson's coefficient and / or Spearman's coefficient will be used.

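### Thirty people of widely differing motor ability are allocated with no restriction or stratification described and compared without covariates, leaving avoidable chance imbalance in stepping ability

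*Combined protocol and SAP*

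**What the plan says.** All of this is in section 6, Material and methods, of the combined protocol and SAP.

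- **Size.** "30 participants will be recruited", and "No sample calculation will be performed as it is a convenience sample for a pilot study".
- **Entry.** The motor criteria are "Clinical symptoms of hemiplegia or hemiparesis" and "Score equal to or less than 10 in the Spanish version of the Trunk Impairment Scale 2.0". The second is a ceiling with no floor. Participants also need "Ability to understand and execute simple instructions". Neither list sets a walking level, a Barthel or Rankin range, or an upper limit on time since stroke.
- **Allocation.** The whole description is that "the randomization between the experimental group and the control group will be done by computerized lottery". No ratio, blocking, stratification or minimisation is mentioned.
- **Outcomes.** These include the Barthel Index, the Rankin scale, falls and gait, and "Standing balance: Spanish version of the Postural Assessment Scale for Stroke Patients, Berg Scale". Gait starts with the stepping section of the Brunel Balance Assessment, and only those who reach 6 go on to the accelerometer. The plan therefore expects people on both sides of that line.
- **Between-group analysis.** The change in each arm is compared by Student's t or Mann-Whitney test at the 0.05 level. No covariate is named.

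**The concern.** Stepping ability plausibly governs how far a person can move on the outcomes of hypotheses (c) to (e) in section 5: activities of daily living, standing balance, falls and gait. A person who cannot step has little room to change on a stepping test and contributes no accelerometer data. Exposure to falls also differs.

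If the two kinds of participant are split unevenly, part of any difference between arms reflects the mix rather than the App. If mean change differs by D between those who do and do not reach score 6, a 20-point difference in mix shifts the unadjusted contrast by 0.20 × D. The plan gives no figure for D.

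For the accelerometer measures the problem takes another form. The comparison is confined to those who reach 6, so chance sets how many of them each arm has.

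Neither the described allocation nor the described analysis deals with this. It matters because the plan applies significance tests, and section 7 says that good adherence together with better results than conventional therapy would support considering the App as a new tool.

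**Working it through.** **Inputs.** N = 30 (section 6). The ratio is not stated, so 1:1 is assumed. The number W reaching stepping score 6 is not stated, so 6 to 24 of 30 (20% to 80%) is assumed. The plan has no figure to reproduce, because the sample size was not calculated.

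**Two readings of the lottery.**

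- *Simple:* each person has probability 0.5. The App arm size n is Binomial(30, 0.5). Given n, the number x in that arm who reach score 6 is hypergeometric (30, W, n).
- *Fixed:* 15 of 30 are drawn. Then n = 15 and x is hypergeometric (30, W, 15).

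In both, the difference in share is |x/n − (W − x)/(30 − n)|, and the probabilities of all outcomes at or beyond the threshold are added.

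**Chance of a difference in share at least this large** (W and 30 − W give the same result):

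| W of 30 | Simple, ≥10 points | Simple, ≥20 | Simple, ≥30 | Fixed 15:15, ≥20 | Fixed 15:15, ≥30 |
|---|---|---|---|---|---|
| 6 or 24 | 53.8% | 17.8% | 4.6% | 16.9% | 1.7% |
| 9 or 21 | 60.8% | 26.8% | 7.9% | 42.7% | 10.9% |
| 12 or 18 | 60.5% | 29.2% | 11.2% | 26.4% | 6.0% |
| 15 | 58.5% | 36.2% | 11.2% | 46.6% | 14.3% |

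*Hand check, W = 15, fixed 15:15.* A difference of 20 points or more needs |2x − 15| ≥ 3, so x is not 7 or 8. The probability is 1 − 2 × 6435² / 155,117,520 = 1 − 0.534 = 0.466.

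The fixed columns jump because only a few differences are possible. With odd W they are 1/15, 3/15, 5/15 and so on, so exactly 20 points counts. With even W they are 0, 2/15, 4/15 and so on. The jumps do not mean that a fixed draw is worse than a simple one.

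At every whole number from 6 to 24, rather than steps of three, the 20-point ranges are unchanged and the 10-point range under simple allocation widens from 54–61% to 52–63%.

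**Accelerometer subset.** If 12 people reach score 6, the chance that one arm has 3 or fewer of them is 2 × P(Binomial(12, 0.5) ≤ 3) = 14.6% under simple allocation, and 6.0% under a fixed 15:15 draw.

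**Arm size, simple allocation only.** The chance of exactly 15:15 is 14.4%, of 13:17 or worse 58.5%, of 12:18 or worse 36.2%, and of 10:20 or worse 9.9%. The standard error relative to 15:15 is √[(1/a + 1/b)/(2/15)]. At 12:18 this is 1.021. At 10:20 it is √(0.15/0.1333) = 1.061.

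**Effect of stratifying.**

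- *One draw within each stratum, all enrolled first.* If W is even, the split is exact. If W is odd, each stratum is off by one in opposite directions and the difference is 1/15 = 6.7 points. Arms are 15:15 in both cases.
- *Blocks of 4 within strata* (5,000 simulated runs per value of W). The largest difference was 5 to 11 points, the worst split was 14:16, and no run reached 20 points. Check at W = 6: strata of 4:2 and 12:12 give 4/16 − 2/14 = 10.7 points.
- *Blocks of 4 and 6 mixed* (5,000 runs per value of W in steps of three). A 20-point difference occurred in at most 0.06% of runs. It needs both strata to stop halfway through a block of 6, unbalanced in opposite directions.

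**The case against.** The strongest reply is that the plan never calls its lottery unrestricted. A computerised draw of 15 from 30 fits the words equally well. It is also practicable, since the plan says that 30 is close to the centre's whole stroke caseload and a full list could exist before allocation. This stands, and it removes the arm-size issue. It does not remove imbalance in stepping ability, which is still 20 points or more with probability 17% to 47%.

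Four further points limit what can be claimed.

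- A reader might infer that marked imbalance is likely. It is not: each 20-point figure is below one half. Only modest imbalance, 10 points or more under simple allocation, is more likely than not.
- A reader might infer that nothing in the analysis helps. Comparing change does remove a difference in starting level. What remains is differing room for change, and the documents give no figure for its size.
- A reader might take entry as open to everyone. It is limited by the trunk score, by the need to follow simple instructions and by the exclusions. The range is wide, not unlimited.
- The documents do not define what a stepping score of 6 means, so it should not be equated with being a walker. It is the plan's own threshold for accelerometer gait testing, which is reason enough to balance on it.

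It is also fair to say that this is a pilot on a convenience sample and that no result from 30 people would be definitive. That lowers the stakes, but the plan still tests effectiveness and intends to act on the answer.

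**Conclusion.** The concern holds as a matter of avoidable noise. With 30 people, no described restriction or stratification and no covariate in the comparison, the share reaching stepping score 6 differs between arms by 20 points or more with probability 18% to 36% (simple 1:1) or 17% to 47% (fixed 15:15). The 1:1 ratio and the range of 6 to 24 of 30 are assumptions, since the plan gives neither.

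Two stronger conclusions are not supported. First, the trial is not biased by this: randomisation balances the arms on average, and the cost is lost precision and a single result that is hard to interpret. Second, unequal arm size is not a serious harm. Even 10:20, which with worse splits has a chance of 9.9%, raises the standard error by only about 6%, and chance is as likely to give more App users as fewer.

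The change is worth making because it is cheap and uses a measure already in the plan. The trial is not invalid without it.

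**What to change.** 1. State the ratio (1:1) and how the sequence is generated and concealed.
2. Score the Brunel stepping section at baseline, before allocation, and stratify by score 6 reached, yes or no. Two strata are workable with 30 people.
3. If all participants can be enrolled first, make one stratified draw. This leaves no sequence to guess. If enrolment is staggered, use concealed permuted blocks of varying size without blocks of 2, or minimisation with a random element. A block of 2 gives away its second allocation in an open-label, single-centre trial.
4. Replace the unadjusted t or Mann-Whitney comparison of change with a model that includes the stratification factor and, where one exists, the baseline value of the outcome. ANCOVA is an example for the scale scores. The number of falls needs the equivalent for a count. For accelerometer outcomes restricted to those who reached 6 at baseline, the factor is constant and drops out.

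**Cost.** One assessment moves ahead of allocation, the randomisation program needs a different setting, and the model spends one or two degrees of freedom. Some allocations remain predictable if blocks are used.

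### Falls are a count with no stated window or time at risk, yet the visit-based comparison and carry-forward rules are not waived for them, so unequal dropout can bias the between-arm estimate in either direction

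*Combined protocol and SAP*

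**What the plan says.** Section 5, hypothesis d, claims that the App exercises will "improve the balance in sitting and standing and reduce the number of falls of individuals who have suffered a stroke" compared with usual monitoring. The only description of the outcome is one line in the section 6 list of variables: "Record of the number of falls". It gives no period over which falls are counted, no baseline look-back, no method of collection and no time at risk.

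The statistical paragraph of section 6 sets one analysis for all variables. It looks at the "difference between means and standard deviations of the variables both at the initial time and at 6 and 12 weeks". Within groups, "Its statistical significance will be calculated by the Student's t test or the Mann-Whitney U test for paired data". For effectiveness, "the evolution obtained in the different groups will be compared with the same statistical tests for independent samples". On missing data, "the missing data will be imputed applying the imputation criterion of the last observation made", and the analysis set is everyone: "all subjects will be included, regardless of subsequent events such as protocol violations, lost data, or loss to follow-up". Falls are not named in this paragraph and are not exempted from any part of it. Neither a rate, nor follow-up time, nor a count model appears anywhere.

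**The concern.** A Barthel or Berg score has a value on the day of the visit. A falls count has a value only once a window is fixed, and its expected size is the fall rate times the length of that window. The plan's rule was written for scores and passes over this.

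Two problems follow. First, for a participant who leaves early, carry-forward misstates the count. If the count accumulates from randomisation, the carried value treats the weeks after exit as fall-free. If the count refers to an interval, or the carried value is a baseline look-back, the rule supplies falls that were never observed. When one arm loses more people than the other, the error does not cancel. This is a realistic possibility, since only the App arm is asked to do extra exercises on five days a week for three months.

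Second, the paired baseline-to-follow-up test is meaningful for falls only if the two windows have the same length, and the plan sets neither.

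At stake is the falls part of hypothesis d. Section 7 says that better results than conventional therapy would support considering the App as a new tool, and an artefact in the falls result could feed that conclusion.

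**Working it through.** The plan states no fall rate, dropout or power figure, so there is nothing of its own to reproduce.

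**Inputs from section 6:** visits at 0, 6 and 12 weeks; 30 participants; significance level 0.05. **Assumed:** 15 per arm (the allocation ratio is not given), two-sided tests, the same constant fall rate in both arms (no true effect), 1 to 4 falls per person-year, gamma-Poisson counts with shape 1, and the dropout values shown. Simulated figures use 2,000 runs per scenario.

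**1. Cumulative count, falls logged up to exit.** With a share *d* leaving uniformly over the 12 weeks, the mean fraction of time observed is 1 − *d*/2. The App/control count ratio is the ratio of these fractions.

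- 20% vs 7%: 0.90 / 0.965 = 0.93
- 33% vs 7%: 0.835 / 0.965 = 0.87
- 20% vs 20%: 0.90 / 0.90 = 1.00

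**2. Cumulative count, falls recorded only at visits.** A person leaving after week 6 keeps 6 of 12 weeks; a person leaving before week 6 keeps the starting value of zero. With dropout in the App arm only, the ratio is 1 − *d*/2 if all leave late (0.90 at 20%, 0.80 at 40%) and 1 − *d* if all leave early (0.80, 0.60). If exits are uniform, half are early and half late, so the retained fraction is 1 − *d*(½ × 1 + ½ × ½) = 1 − 0.75*d*. The two contrasts in step 1 then become 0.85 / 0.9475 = 0.90 and 0.7525 / 0.9475 = 0.79.

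**3. Six-week interval count, with a baseline look-back of *L* weeks carried forward.** An early leaver is given a change of zero. Everyone else has an expected change of *r* × (6 − *L*)/52 at *r* falls per year. The App-minus-control shift in mean change is therefore *d*(early) × *r* × (*L* − 6)/52. With 20% dropout in the App arm only, half of it early:

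- *r* = 1, *L* = 26: 0.10 × 1 × 20/52 = +0.04 falls
- *r* = 4, *L* = 52: 0.10 × 4 × 46/52 = +0.35 falls

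Simulation gives the same range. The sign is opposite to steps 1 and 2: the App arm shows a smaller reduction. With *L* = 6 the expected shift is zero, and simulation showed no material shift.

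**4. Size against noise.** With 40% dropout in the App arm only (half early, half late) and a cumulative count, the between-arm t and Mann-Whitney tests reject in about 5–10% of null runs, against about 4–6% with no dropout. At 0.75 falls per person per 12 weeks, the standard error of the log rate ratio is √[2 × (1/0.75 + 1)/15] = 0.56, so a 95% CI runs a factor of about exp(1.96 × 0.56) = 3 either way. A ratio of 0.93 is |ln 0.93| / 0.56 = 0.13 standard errors from 1.

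**5. Within-group test.** The apparent change is (follow-up window / look-back) − 1. The last column is the paired t test with n = 15 under no effect, over 1 to 4 falls per year.

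| Look-back (weeks) | vs 6-week window | vs 12-week cumulative | Paired t rejects (vs 6 weeks) |
|---|---|---|---|
| 6 | 0% | +100% | 1–4% |
| 12 | −50% | 0% | 6–22% |
| 26 | −77% | −54% | 30–85% |
| 52 | −88% | −77% | 76–99% |

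A look-back of the same length in both arms shifts both arms equally and so does not, by itself, move the between-arm contrast.

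**The case against.** The statistical paragraph never mentions falls, and reading its word for evolution as a change score is an inference, though the natural one. The one-line outcome entry is compatible with a prospective log kept over the same 12 weeks in both arms. On equal and complete windows, a rank test on counts is valid. The between-arm figures depend on assumed differential dropout and are small beside the sampling error of a 30-person pilot. Falls are one of many outcomes, and no sample size was calculated for any of them.

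Most of this stands, and it limits the point. It does not remove it: even with a prospective log, carry-forward applies as written to anyone who leaves, and no exposure time is recorded to correct for it.

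A reader might go further and infer that the plan builds in a spurious fall reduction of up to 88%. The documents do not support that. They state no look-back, so unequal windows are a possibility left open and not a feature of the plan. Against a 12-week count, a 13-week look-back would give only 1 − 12/13 = 8%. The artefact also belongs to the within-group test, whereas hypothesis d is comparative and section 6 assigns effectiveness to the between-group comparison. Nor do the documents support the inference that the error always favours the App, since step 3 of the working shows it reversing.

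**Conclusion.** The point holds as a gap in definition combined with a stated rule that does not suit the variable. The counting window and time at risk for falls are undefined, and carry-forward would misstate the count for anyone who leaves early.

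Under equal true rates, the between-arm count ratio would be about 0.93 at 20% vs 7% dropout and about 0.87 at 33% vs 7%, if falls are logged to exit. It would be further from 1 if they are recorded only at visits, and the error could go against the App if a long baseline count is carried forward. A cumulative count with equal dropout gives no between-arm bias. The damage is to the estimate and its interpretation, with little rise in between-arm false positives. The within-group paired test is exposed only if the look-back and follow-up windows differ in length. All dropout and fall rates here are assumptions.

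A reader might also infer that a rate ratio would settle the matter. It equals 1.00 under no effect only if leaving is unrelated to fall risk. Section 6 lists lower-limb fracture, a second stroke and worsening disease among its exclusions, beside death, which can only follow entry. If these also end follow-up, exit and falls may be linked. The effect is confined to the falls part of hypothesis d and does not undermine the trial as a whole.

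**What to change.** Before data collection, state in section 6 that:

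- falls are counted prospectively from randomisation to week 12, by the same method in both arms;
- days observed and the reason for leaving are recorded for every participant;
- falls are exempt from last-observation carry-forward and from the paired baseline-to-follow-up test;
- falls per person-time are reported by arm, with a rate ratio and 95% CI, for example from Poisson regression with robust variance or negative binomial regression with log person-time as offset, together with a permutation p-value;
- any baseline fall rate is used only as a covariate, with its look-back stated;
- the result is exploratory at n = 30.

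The cost is a few lines of text, one extra field on the case report form and one model. There are two downsides. With about 15 per arm and few falls, model standard errors are fragile, which is why the permutation p-value is added. And the offset does not remove bias if people leave for reasons tied to falling, so the recorded reasons should be tabulated by arm beside the rate ratio. The window has to be fixed now, because exposure time that was not recorded is hard to recover later.
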